**Sponsor/Quotient Sciences Confidential**

Medicines for Malaria Venture  
Protocol: MMV\_MMV367\_21\_01

Page x of y

TABLE 14.1.3.2  
Demographic and Baseline Characteristics  
Summary Statistics: Safety Analysis Set  
Part 2

	n	Treatment Sequence		
		Fed/Fasted (N=X)	Fasted/Fed (N=X)	Overall (N=X)
Age (years)	n	xx	xx	xx
	Mean	xx.xx	xx.xx	xx.xx
	SD	xx.xx	xx.xx	xx.xx
	Median	xx.xx	xx.xx	xx.xx
	Min	xx.x	xx.x	xx.x
	Max	xx.x	xx.x	xx.x
Ethnicity n(%)	<All categories on source>	xx (xx.x)	xx (xx.x)	xx (xx.x)
Race n(%)	<All categories on source>	xx (xx.x)	xx (xx.x)	xx (xx.x)
Sex n(%)	Male	xx (xx.x)	xx (xx.x)	xx (xx.x)
	Female	xx (xx.x)	xx (xx.x)	xx (xx.x)
Height (cm)	...	...	...	...
Weight (kg)	...	...	...	...
BMI (kg/m  )	...	...	...	...

Note: The data in this table are presented in listing xx

All subjects were to receive both treatments (i.e., Regimen 6 and Regimen 7) in a randomised manner over the two separate dosing occasions

PROGRAM PATH: X:\~\QSC207031\~\TFLS\PRODUCTION\TAB-XX

DDMMYYYY HH:MM

Programming note: This table will continue for all categories of ethnicity and race  
Height, Weight and BMI will be assessed using the same descriptive statistics as Age  
If any values are missing, then a "missing" row will be included in the table, as applicable

**Sponsor/Quotient Sciences Confidential**

Medicines for Malaria Venture  
Protocol: MMV\_MMV367\_21\_01

Page x of y

TABLE 14.1.4.1  
Lifestyle Details: Smoking History and Alcohol Consumption  
Summary Statistics: Safety Analysis Set  
Part 1

		Active Dose of MMV367				
		ALL PLACEBO (N=XX) n (%)	ALL ACTIVE (N=XX) n (%)	100 mg (N=XX) n (%)	300 mg (N=XX) n (%)	.....
Does the participant smoke (1)		NO PREVIOUSLY	xx (xx.x) xx (xx.x)	xx (xx.x) xx (xx.x)	xx (xx.x) xx (xx.x)	xx (xx.x) xx (xx.x)
Alcohol Consumption (2)		NONE YES: NOT EXCESSIVE	xx (xx.x) xx (xx.x)	xx (xx.x) xx (xx.x)	xx (xx.x) xx (xx.x)	xx (xx.x) xx (xx.x)

Note: The data in this table are presented in listing xx

All subjects were planned to receive a single dose of either MMV367 or matching placebo

All Placebo/All Active relate to placebo or active subjects pooled over all cohorts, respectively

(1) Smoked or used e-cigarettes or nicotine replacement products in the last 12 months

(2) Regular alcohol consumption (>21 units/week in males and >14 units/week in females)

1 unit = 1/2 pint beer, 25 mL of 40% spirit, 1.5 to 2 units = 125 mL glass of wine depending on type

PROGRAM PATH: X:\~\QSC207031\~\TFLS\PRODUCTION\TAB-XX

DDMMYYYY HH:MM

Programming note: A similar table will be produced for Part 3, i.e., Table [14.1.4.3]

**Sponsor/Quotient Sciences Confidential**

Medicines for Malaria Venture  
Protocol: MMV\_MMV367\_21\_01

Page x of y

TABLE 14.1.4.2  
Lifestyle Details: Smoking History and Alcohol Consumption  
Summary Statistics: Safety Analysis Set  
Part 2

		Treatment Sequence		
		Fed/Fasted (N=X)	Fasted/Fed (N=X)	Overall (N=X)
Does the participant smoke? (1)	NO PREVIOUSLY	xx (xx.x)	xx (xx.x)	xx (xx.x)
		xx (xx.x)	xx (xx.x)	xx (xx.x)
Alcohol Consumption (2)	NONE	xx (xx.x)	xx (xx.x)	xx (xx.x)
	YES: NOT REGULARLY	xx (xx.x)	xx (xx.x)	xx (xx.x)

Note: The data in this table are presented in listing xx  
All subjects were to receive both treatments (i.e., Regimen 6 and Regimen 7) in a randomised manner  
over the two separate dosing occasions  
(1) Smoked or used e-cigarettes or nicotine replacement products in the last 12 months  
(2) Regular alcohol consumption (>21 units/week in males and >14 units/week in females)  
1 unit = 1/2 pint beer, 25 mL of 40% spirit, 1.5 to 2 units = 125 mL glass of wine depending on type

PROGRAM PATH: X:\~\QSC207031\~\TFLS\PRODUCTION\TAB-XX

DDMMYYYY HH:MM

**Sponsor/Quotient Sciences Confidential**

Medicines for Malaria Venture  
Protocol: MMV\_MMV367\_21\_01

Page x of y

TABLE 14.1.5.1  
Extent of Exposure  
Summary Statistics: Safety Analysis Set  
Part 1

Treatment	Subjects Dosed (N=XX)
	n (%)
ALL PLACEBO	xx (xx.x)
ALL ACTIVE	xx (xx.x)
100 mg	xx (xx.x)
...	...

Note: The data in this table are presented in listing x.x  
All subjects were planned to receive a single dose of either MMV367 or matching placebo  
All Placebo/All Active relate to placebo or active subjects pooled over all cohorts, respectively

PROGRAM PATH: X:\~\QSC207031\~\TFLS\PRODUCTION\TAB-XX

DDMMYYYY HH:MM

**Sponsor/Quotient Sciences Confidential**

---

Medicines for Malaria Venture  
Protocol: MMV\_MMV367\_21\_01

Page x of y

TABLE 14.1.5.2  
Extent of Exposure  
Summary Statistics: Safety Analysis Set  
Part 2

Treatment	Subjects Dosed (N=X)
	n (%)
XX mg FAST	xx (xx.x)
XX mg FED	xx (xx.x)

---

Note: The data in this table are presented in listing x.x  
All subjects were to receive both treatments (i.e., Regimen 6 and Regimen 7) in a randomised manner  
over the two separate dosing occasions

PROGRAM PATH: X:\~\QSC207031\~\TFLS\PRODUCTION\TAB-XX

DDMMYYYY HH:MM

**Sponsor/Quotient Sciences Confidential**

Medicines for Malaria Venture  
Protocol: MMV\_MMV367\_21\_01

Page x of y

TABLE 14.1.5.3.1  
Extent of Exposure: Subjects Dosed by Day  
Summary Statistics: Safety Analysis Set  
Part 3

Day	ALL PLACEBO	XX mg	XX mg	XX mg
	(N=xx)	(N=xx)	(N=xx)	(N=xx)
	n (%)	n (%)	n (%)	n (%)
DAY 1	xx (xx.x)	xx (xx.x)	xx (xx.x)	xx (xx.x)
DAY 2	xx (xx.x)	xx (xx.x)	xx (xx.x)	xx (xx.x)
...	...	...	...	...

Note: The data in this table are presented in listing xx

All subjects were planned to receive a single dose of either MMV367 or matching placebo over 3 days

All Placebo/All Active relate to placebo or active subjects pooled over all cohorts, respectively

PROGRAM PATH: X:\~\QSC207031\~\TFLS\PRODUCTION\TAB-XX

DDMMYYYY HH:MM

**Sponsor/Quotient Sciences Confidential**

Medicines for Malaria Venture  
Protocol: MMV\_MMV367\_21\_01

Page x of y

TABLE 14.2.1.1.1  
Excretion: MM367  
Ae(Urine) by Collection Period <(units)>  
Summary Statistics: PK Analysis Set  
Part 1

MMV367 (N=XX)

Collection Period	n	Mean	SD	CV%	Median	Min	Max
PRE-DOSE	xx	xx.xx	xx.xx	xx.x	xx.xx	xx.x	xx.x
TIME0 - TIME1	xx	xx.xx	xx.xx	xx.x	xx.xx	xx.x	xx.x
TIME1 - TIME2	xx	xx.xx	xx.xx	xx.x	xx.xx	xx.x	xx.x
TIME2 - TIME3	xx	xx.xx	xx.xx	xx.x	xx.xx	xx.x	xx.x
...	...	...	...	...	...	...	...
<All other time intervals>	xx	xx.xx	xx.xx	xx.x	xx.xx	xx.x	xx.x

Note: The data in this table are presented in listing xx  
All subjects were planned to receive a single dose of either MMV367 or matching placebo  
All Placebo/All Active relate to placebo or active subjects pooled over all cohorts, respectively  
Where a participant has failed to void or has a ND concentration over a particular collection interval, the amount excreted (Ae) has been set to zero

PROGRAM PATH: X:\~\QSC207031\~\TFLS\PRODUCTION\TAB-XX

DDMMYYYY HH:MM

(Programming Note: This table will be continued for all collection periods  
A similar table will be produced for:  
• %Ae(Urine) (Recovery), i.e., Table [14.2.1.1.3]

**Sponsor/Quotient Sciences Confidential**

Medicines for Malaria Venture  
Protocol: MMV\_MMV367\_21\_01

Page x of y

TABLE 14.2.1.1.2

Excretion: MMV367

Cumulative Ae(Urine) <(units)>

Summary Statistics: PK Analysis Set

Part 1

MMV367 (N=XX)

Collection Period	n	Mean	SD	CV%	Median	Min	Max
PRE-DOSE	xx	xx.xx	xx.xx	xx.x	xx.xx	xx.x	xx.x
TIME0 - TIME1	xx	xx.xx	xx.xx	xx.x	xx.xx	xx.x	xx.x
TIME0 - TIME2	xx	xx.xx	xx.xx	xx.x	xx.xx	xx.x	xx.x
TIME0 - TIME3	xx	xx.xx	xx.xx	xx.x	xx.xx	xx.x	xx.x
...	...	...	...	...	...	...	...
<All other time intervals>	xx	xx.xx	xx.xx	xx.x	xx.xx	xx.x	xx.x

Note: The data in this table are presented in listing x.x

All subjects were planned to receive a single dose of either MMV367 or matching placebo

All Placebo/All Active relate to placebo or active subjects pooled over all cohorts, respectively

PROGRAM PATH: X:\~\QSC205477\~\TFLS\PRODUCTION\TAB-XX

DDMMYYYY HH:MM

(Programming note: This table will be continued for all collection periods. If required, as a result of early withdrawal or varying follow-up periods, this table will be produced using the LOCF approach. A similar table will be produced for

- Cumulative %Ae(Urine) (Recovery), i.e., Table [14.2.1.1.4]

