**Sponsor/Quotient Sciences Confidential**

---

- XX mg MMV367 fed [Regimen 7] (test) vs XX mg MMV367 fasted [Regimen 6] (reference)

Renal clearance (CLr) is a plasma parameter and will be calculated as follows in Part 1, if applicable:

$$CL_r = \frac{Ae}{AUC}$$

where both amount excreted (Ae) of parent in urine and AUC of parent in plasma are determined over co-incident time ranges after dosing. For example, if urinary Ae is calculated over 0-24 hours then the plasma AUC used will also be calculated over the same period. Details of methods for calculation of CumAe are included in [Section 9.2](#).

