**Table 10 Urine PK Parameter Definitions and Rounding Specifications**

Parameter	Definition	Unit	DP	No. of DP
Ae	Amount excreted	mass unit	DP	2
CumAe	Cumulative amount excreted	mass unit	DP	2
%Ae	Percentage of dose excreted	%	DP	2
Cum%Ae	Cumulative percentage of dose excreted	%	DP	2

DP = decimal places

Dose is defined as per [Table 7](#)

Urine PK parameters will be calculated as follows:

- When converting urine collection weights to urine volume (if required), the following conversion factor will be used:

$$1.02 \text{ g of urine} = 1 \text{ mL of urine}$$

This will be calculated in SAS as follows:

$$\text{Urine weight (g)} / 1.02 = \text{Urine volume (mL)}$$

- If MMV367 concentrations in urine are provided in mass unit/g the following conversion will be performed using SAS:

$$\text{Concentration (mass units/g)} * 1.02 = \text{Concentration (mass units/mL)}$$

- Ae will be derived for each collection period:

$$Ae = \text{concentration} * \text{volume}$$

- CumAe, will be calculated by the incremental summation of the Ae over all collection periods. Note: The amount excreted in the pre-dose sample should not be included in the calculation of the cumulative amount excreted.
- %Ae will be derived for each collection period:

$$\%Ae = 100 * Ae / \text{Total Dose Administered}$$

- Cum%Ae will be calculated by the incremental summation of the %Ae over all collection periods. Note: The percentage of dose excreted in the pre-dose sample will not be included in the calculation of the cumulative percentage of dose excreted.
- Where a participant has failed to void over a particular collection interval the Ae for that collection interval will be set to zero.
- If part of a void over a particular collection interval is missing due to spillage or accidental discarding, the Ae will still be calculated providing other samples have

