## **Sponsor/Quotient Sciences Confidential**

---

been collected within the interval. Where no other samples are collected within the interval the concentration will be set to missing for the purposes of the calculation urine PK parameters. In both scenarios the data will be flagged to highlight a missing void. Affected participant(s) may be excluded from summary statistics, this will be documented as part of the PK population.

- Imputation of non-numerical values reported in the urine dataset (i.e., concentrations that are BLQ) will be entered as zero for calculation of urine PK parameters.

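### If urine data are reported, the SAP's carry-forward note and lost-void rule can understate urinary recovery, and the lost-void rule can also lower renal clearance

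*SAP*

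**What the plan says.** Three places in the SAP bear on this.

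- **Carry-forward.** The programming note under mock Table 14.2.1.1.2 in SAP 21 says: "If required, as a result of early withdrawal or varying follow-up periods, this table will be produced using the LOCF approach". It asks for a similar table for cumulative percentage recovery (14.2.1.1.4).
- **Lost urine.** SAP 9.2.1 says: "If part of a void over a particular collection interval is missing due to spillage or accidental discarding, the Ae will still be calculated", on condition that other samples were kept in the interval. Otherwise, "Where no other samples are collected within the interval the concentration will be set to missing". It adds "In both scenarios the data will be flagged to highlight a missing void" and "Affected participant(s) may be excluded from summary statistics, this will be documented as part of the PK population". A genuine failure to void gives Ae = 0. Accumulation is defined by "CumAe, will be calculated by the incremental summation of the Ae over all collection periods", with no statement of what happens when one of the terms is missing.
- **Renal clearance.** SAP 9.1.1 defines CLr as Ae/AUC, where both "are determined over co-incident time ranges after dosing". Its example pairs 0-24 h urine with 0-24 h plasma, and it refers to SAP 9.2 for the calculation of CumAe.

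SAP 6.3 and 9.2 both state that urine handling is not currently a planned analysis for the CSR. The rules apply if a validated method is developed and the sponsor wants the data reported.

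**The concern.** Cumulative excretion keeps rising while drug remains in the body. A carried-forward value treats the rest of the collection as zero, and nothing in the table would show this. The SAP's flag covers missing voids rather than carried values, and the shell has a single n column, so carried and observed values would look alike.

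The lost-void rule has a related weakness. The interval amount is computed from the urine that was kept, so it falls short by the amount lost. Plasma AUC still covers the whole interval, so CLr falls short too. Whether to drop the participant is left to discretion, without a criterion, and is documented with the PK population, which SAP 6.3 confirms after all PK parameters have been derived. The choice would therefore be made with the results visible. For plasma, by contrast, SAP 9.1.3 fixes its exclusions in advance: adjusted r-squared below 0.8, or more than 20% of AUC(0-inf) extrapolated.

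At stake is an exploratory description of the fraction excreted unchanged and of CLr, from six active participants in each of Cohorts 1C and 1D. A few incomplete collections would shift it towards little renal elimination.

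**Working it through.** The documents give no figure for urinary recovery or CLr, so there is none to reproduce. The sizes below are illustrations.

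**Inputs.** Predicted half-life 19 h (Protocol 5.3.1.2). Collection intervals 0-6, 6-12, 12-24, 24-48 and 48-72 h (Protocol Appendix 5; SAP Appendix 4). Six active participants per cohort (SAP 5.3), with a planned minimum of four (Protocol 8.1.1). Assumed here: a half-life range of 10 to 40 h, rapid absorption, first-order elimination, urinary excretion proportional to plasma AUC, the stopping time, and the share of urine lost.

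**Formula.** Share of eventual excretion reached by time t: S(t) = 1 - 2^(-t/half-life). At 19 h: S(12) = 0.355, S(24) = 0.583, S(48) = 0.826, S(72) = 0.928.

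**1. Carry-forward and cumulative recovery.** Bias in the 0-72 h value = S(T)/S(72) - 1, where T is the last collection. The effect on a group mean takes the other participants as complete and equal in true recovery, so it is the individual bias divided by the group size.

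| Last collection | Half-life 19 h | 10 h | 40 h | Mean of 6 (19 h) |
|---|---|---|---|---|
| 24 h | -37.1% | -18.4% | -52.3% | -6.2% |
| 48 h | -10.9% | -2.9% | -20.8% | -1.8% |

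For T = 24 h at 19 h, 0.583/0.928 = 0.629, and 37.1/6 = 6.2. Over 10 to 40 h the effect on a mean of six is 3.1% to 8.7%. With four participants it is 37.1/4 = 9.3% at 19 h.

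**2. Carry-forward and CLr.** If excretion is proportional to AUC, Ae(0-T) = CLr × AUC(0-T) for any T. A participant who stops at 24 h has Ae(0-24)/AUC(0-24) = CLr, so the bias is 0%. A shortfall would arise only if the carried 0-24 h amount were divided by AUC(0-72), and SAP 9.1.1 rules that pairing out.

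**3. Part-lost void.** If a fraction f of the amount in interval (a, b) is lost, Cum%Ae(0-72) and CLr(0-72) both change by -f × [S(b) - S(a)]/S(72). With f = 0.5 in 12-24 h at 19 h: 0.5 × (0.583 - 0.355)/0.928 = 0.123, or 12% too low (10.7% at 40 h, 12.4% at 10 h). The mean of six is 2.1% too low. The time ranges match nominally, but the numerator does not contain all the urine from its range. Excluding the participant removes the bias.

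**4. Wholly lost interval.** The concentration is missing, and two readings of the sum are open. If the sum skips the gap, losing all of 12-24 h lowers Cum%Ae(0-72) by 24.7% at 19 h. If missingness carries through to later sums, nothing is understated. The SAP does not choose between them.

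**The case against.** The strongest reply is that little of this is likely to happen and that safeguards exist. The urine analysis is optional and exploratory, depends on a future assay, and would appear in an addendum or separate report. No dose decision, safety rule or higher-ranked objective uses it. Collection ends at 72 h, while participants stay in the unit to Day 5 (96 h), so withdrawal before 72 h should be uncommon. Varying follow-up does not arise from the fixed Part 1 schedule. The shell's program path names study QSC205477, where the neighbouring shells name QSC207031, so the note may be leftover template text. SAP 9.2 itself does not call for carry-forward. Lost voids are flagged, and affected participants can be excluded.

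These points stand, and they keep the severity low. They do not make the rules right once triggered. The flag does not reach carried-forward values, optional exclusion is not a rule, and the 96 h evaluability definition that might remove early withdrawals is not used at reporting (SAP 3.2.1).

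Three stronger readings are tempting, and the documents do not support them:

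- A reader might infer that carry-forward also understates CLr. The co-incident ranges in SAP 9.1.1, and the absence of carry-forward from SAP 9.2, prevent that.
- A reader might infer that a wholly lost interval necessarily shortens every later cumulative value. The SAP sets it to missing and leaves the sum undefined, so this is a gap in specification, not a demonstrated bias.
- A reader might infer that reported recovery will be understated as a matter of course. Both rules are conditional, so the most that can be said is that it can be.

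**Conclusion.** The point holds as a conditional, low-severity defect. If urine data are reported and a participant withdraws before 72 h, carry-forward gives a lower bound presented as an observed value: about 37% too low for that participant after a 24 h stop, and about 6% too low for a mean of six. If part of a void is lost and the participant is kept, Ae, Cum%Ae and CLr all fall by the lost share, about 12% over 0-72 h in the assumed case. The treatment of a wholly lost interval is unspecified. The sizes rest on a predicted half-life, a simple one-compartment model, and assumed stopping times and losses. The direction of the two biases does not depend on those choices, provided excretion continues after the last collection and the lost urine contained drug.

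**What to change.** In SAP 21, delete the carry-forward note from Table 14.2.1.1.2, and so from 14.2.1.1.4. In SAP 9.2.1:

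- set Ae and %Ae to missing for any interval with a known lost void, in part or whole;
- set CumAe and Cum%Ae to missing from that interval onward, which also settles the wholly lost case;
- summarise cumulative recovery at each time only in participants with complete collection to that time, and show n;
- keep Ae = 0 for a genuine no-void interval;
- list incomplete values with their flag.

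In SAP 9.1.1, calculate CLr only over intervals with complete urine, using the matching plasma AUC. SAP Table 5 already defines AUC to 24, 48 and 72 h.

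The cost is SAP wording and a shell edit. The downside is a smaller n at late intervals when collections are incomplete.

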**Sponsor/Quotient Sciences Confidential**

Medicines for Malaria Venture  
Protocol: MMV\_MMV367\_21\_01

Page x of y

TABLE 14.2.1.1.5  
Plasma Pharmacokinetic Concentrations: MMV367(<units>)  
Summary Statistics: <PK Analysis Set/PK Analysis Subset>  
Part 1

Treatment	Time Point	Arithmetic (1)							Geometric (2)			
		n	n#	Mean	SD	CV%	Median	Min	Max	Mean	SD	CV%
100 mg (N=XX)	PRE-DOSE	xx	xx	xx.xx	xx.xx	xx.x	xx.xx	xx.x	xx.x	NC	NC	NC
	TIMEPOINT 1	xx	xx	xx.xx	xx.xx	xx.x	xx.xx	xx.x	xx.x	xx.xx	xx.xx	xx.x
	TIMEPOINT 2	xx	xx	xx.xx	xx.xx	xx.x	xx.xx	xx.x	xx.x	xx.xx	xx.xx	xx.x
	...	...	...	...	...	...	...	...	...	...	...	...
	...	...	...	...	...	...	...	...	...	...	...	...
300 mg (N=XX)	PRE-DOSE	xx	xx	xx.xx	xx.xx	xx.x	xx.xx	xx.x	xx.x	NC	NC	NC
	TIMEPOINT 1	xx	xx	xx.xx	xx.xx	xx.x	xx.xx	xx.x	xx.x	xx.xx	xx.xx	xx.x
	TIMEPOINT 2	xx	xx	xx.xx	xx.xx	xx.x	xx.xx	xx.x	xx.x	xx.xx	xx.xx	xx.x
	...	...	...	...	...	...	...	...	...	...	...	...
	...	...	...	...	...	...	...	...	...	...	...	...

Note: The data in this table are presented in listing xx

All subjects were planned to receive a single dose of either MMV367 or matching placebo

All Placebo/All Active relate to placebo or active subjects pooled over all cohorts, respectively

n# indicates the number of subjects with a BLQ value recorded at the time point indicated

(1) For arithmetic summary statistics, concentration values reported as BLQ have been set to zero

(2) For calculation of geometric summary statistics, values reported as BLQ have been set to  $\frac{1}{2} \times \text{LLOQ}$ , except for pre-dose values which will not be summarised. The LLOQ value was <value, units>

PROGRAM PATH: X:\~\QSC207031\~\TFLS\PRODUCTION\tab-XX

DDMMYYYY HH:MM

Programming note: This table will be continued for all treatments and time points

Similar tables will be produced for Part 2 i.e., Table [14.2.1.2.1] and Part 3 i.e., [14.2.1.2.3], with a column for Visit included before time point column.

**Sponsor/Quotient Sciences Confidential**

Medicines for Malaria Venture  
Protocol: MMV\_MMV367\_21\_01

Page x of y

TABLE 14.2.2.1.1  
Plasma Pharmacokinetic Parameters: MMV367  
Summary Statistics: <PK Analysis Set/PK Analysis Subset>  
Part 1

Treatment	Statistic	Parameter 1 (units)	Parameter 2 (units)	Parameter 3 (units)	All Other PK Parameters (units)
100 mg (N=XX)	n	xx	xx	xx	xx
	Mean	xx.x	xx.x	xx.x	xx.x
	SD	xx.x	xx.x	xx.x	xx.x
	CV%	xx.x	xx.x	xx.x	xx.x
	Median	xx.x	xx.x	xx.x	xx.x
	Min	xx	xx	xx	xx
	Max	xx	xx	xx	xx
	Geometric Mean	xx.x	xx.x	xx.x	xx.x
	Geometric SD	xx.x	xx.x	xx.x	xx.x
	Geometric CV%	xx.x	xx.x	xx.x	xx.x
300 mg (N=XX)	...	...	...	...	...
...	...	...	...	...	...

Note: The data in this table are presented in listing xx

All subjects were planned to receive a single dose of either MMV367 or matching placebo

All Placebo/All Active relate to placebo or active subjects pooled over all cohorts, respectively

For concentration parameters, BLQ values will be set to 0 for arithmetic statistics and to  $\frac{1}{2} \times$  LLOQ for geometric statistics>

The LLOQ value was <value, units

PROGRAM PATH: X:\~\QSC207031\~\TFLS\PRODUCTION\TAB-XX

DDMMYYYY HH:MM

Programming note: This table will be continued for all treatments and PK parameters

Similar tables will be produced for Part 2 i.e., Table [14.2.2.1.2] and Part 3, i.e., Table [14.2.2.1.3]  
with a column for Visit included before statistic column.

**Sponsor/Quotient Sciences Confidential**

Medicines for Malaria Venture  
Protocol: MMV\_MMV367\_21\_01

Page x of y

TABLE 14.2.2.2.1  
Plasma Pharmacokinetic Parameters: MMV367  
Statistical Analysis Results - Assessment of Dose Proportionality: <PK Analysis Set/PK Analysis Subset>  
Part 1

		Active Dose of MMV367				
PK Parameter		100 mg (N=XX)	300 mg (N=XX)	750mg (N=XX)	1500mg (N=XX)	2000mg (N=XX)
Cmax (units)	n	xx	xx	xx	xx	xx
	Geometric Mean	xx.x	xx.x	xx.x	xx.x	xx.x
	$\beta$ (90% CI)			x.xx	(x.xx	x.xx)
	$2^\beta$ (90% CI)			x.xx	(x.xx	x.xx)
AUC (0-last) (units)	n	xx	xx	xx	xx	xx
	Geometric Mean	xx.x	xx.x	xx.x	xx.x	xx.x
	$\beta$ (90% CI)			x.xx	(x.xx	x.xx)
	$2^\beta$ (90% CI)			x.xx	(x.xx	x.xx)
AUC (0-inf) (units)	n	xx	xx	xx	xx	xx
	Geometric Mean	xx.x	xx.x	xx.x	xx.x	xx.x
	$\beta$ (90% CI)			x.xx	(x.xx	x.xx)
	$2^\beta$ (90% CI)			x.xx	(x.xx	x.xx)

Note: The data in this table are presented in listing x.x

All subjects were planned to receive a single dose of either MMV367 or matching placebo over 3 days

All Placebo/All Active relate to placebo or active subjects pooled over all cohorts, respectively

Results obtained from log-transformed PK parameters using a power model

The model includes a term for log dose fitted as a fixed effect

The geometric means presented are the same as the geometric means presented in Table [14.2.x.x]. N = total number of subjects in dose group, n = number of subjects with non-missing, valid data,  $\beta$  (ie the slope parameter) and its

90% CI are a measure of dose proportionality,  $2^\beta$  represents the increase in exposure for a 2-fold increase in dose

Dose proportionality can be concluded if the 90% CI for  $\beta$  lie entirely within the critical region (x.xx, x.xx)

PROGRAM PATH: X:\~\QSC207031\~\TFLS\PRODUCTION\TAB-XX

DDMMYYYY HH:MM

